#### **6.1.2.1 Study Procedures**

Table 6.1 summarizes the procedures and assessments to be performed for all patients. Before enrolling a patient, all eligibility criteria must be satisfied.

- Physical examination
- Weight
- ECOG performance status
- Vital signs (blood pressure, pulse, and temperature)
- Disease Assessment
- Concomitant medications and procedures
- Serum chemistry
- Complete blood count (CBC) with differential and platelet count
- Research tissue procurement: collection of biopsy tissue from accessible sites (see schedule)
- Research blood draw: collection of peripheral blood for EBV DNA and correlative biomarker studies (see schedule)
- AE monitoring
- TSH evaluation
- Quality of life assessments (see schedule)
- Administration of intravenous (IV) nivolumab
  - 72-hour window of scheduled nivolumab administration allowed

Study visits will be required on the first day of each cycle.

### **6.1.3 End-of-Treatment Study Procedures**

After having received the last dose of nivolumab on this study, all patients will remain in the study to be followed for safety until the EOT Visit. The EOT Visit should occur 28 ( $\pm$  7) days after the last dose of nivolumab. Patients with ongoing SAEs will be followed until either resolution or stabilization of the event(s) has been determined. Please see Table 6.1 for details of assessments.

- Physical examination
- Weight
- ECOG performance status
- Vital signs (blood pressure, pulse, and temperature)
- Disease Assessment
- Concomitant medications and procedures
- Serum chemistry
- Fasting glucose
- Complete blood count (CBC) with differential and platelet count
- MRI of nasopharynx, face, and neck.
- Whole body PET-CT (top of head to mid-thigh).
- Blood sampling for EBV DNA and exploratory research (see schedule)
- AE monitoring
- Quality of life assessments (see schedule)
- TSH evaluation
- Measurable Disease

### **6.1.4 Post-treatment/Follow-Up Visits**

After completion of all treatment, patients will be followed at 1, 3, 6, and 12 months +/- 1 week for up to 1 year or until disease progression. Please see Table 6.1 for details of assessment.

- Physical examination
- Weight
- ECOG performance status
- Vital signs (blood pressure, pulse, and temperature)
- Concomitant medications and procedures
- Serum chemistry
- Fasting glucose
- Complete blood count (CBC) with differential and platelet count
- MRI of nasopharynx, face, and neck, if applicable (see schedule)
- Whole body PET-CT (top of head to mid-thigh), if applicable (see schedule)
- Blood sampling for EBV DNA and exploratory research, if applicable (see schedule)
- AE monitoring
- Quality of life assessments, if applicable (see schedule)
- TSH evaluation

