Duration of Therapy	Patients will receive 23 weeks of an anticipated total therapy course, although the duration for an individual patient may be extended to as long as 33 weeks to allow for resolution of toxicities.
Duration of Follow-up	Follow-up visits will occur at 1, 3, 6, 9, and 12 months for up to 12 months after end of treatment. Survival follow-up information may be collected via telephone calls or medical records review for an additional 4 years . Survival and disease status will be collected during this 5-year period until participant death, withdrawal, or if the participant is lost to follow-up.
Duration of study	The study will reach completion in 6 years from the time the study opens to accrual.
Study Drugs	Nivolumab will be administered intravenously, at a dose of 240 mg every 14 days. Nivolumab may be held for toxicity but there are no dose reductions.
Safety Assessments	Analyses will be performed for all patients having received at least one dose of study drug. The study will use the CTCAE v5.0 for reporting of non-hematologic adverse events and modified criteria for immune related adverse events. Safety assessments will consist of monitoring and reporting adverse events (AEs) and serious adverse events (SAEs) that are considered related to nivolumab, all events of death, and any study specific issue of concern. The study period during which all AEs and SAEs must be reported begins after informed consent is obtained and study treatment is initiated and ends 12 months following the last administration of study treatment or study discontinuation/termination, whichever is earlier.
Efficacy Assessments	The primary measure of feasibility will be the rate of completion of all adjuvant therapy. This will be determined based on ability to complete all 6 cycles of adjuvant nivolumab without discontinuation for disease progression or toxicity. Secondary measures of efficacy will be clinical response as judged by the investigator; ORR by RECIST 1.1; locoregional control rate, distant metastasis rate, overall survival rate determined by standard physical examination and radiologic imaging; the rate of EBV DNA clearance at end-chemoradiation and at 1 year post-treatment as determined by PCR assay; toxicity assessments graded by CTCAE v5.0 and modified immune related criteria; and quality of life by FACT-NP, FACT-Taxane, HHIE-S, and EuroQOL EQ-5D-3L. Exploratory assessments are self-explanatory.

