### 1.4.2 EBV DNA

Pre-treatment EBV DNA in plasma has been proven to correlate with cancer stage, clinical outcome, and prognosis in patients with endemic NPC. However, post-radiation plasma EBV DNA has an even better correlation with prognosis and has been used to monitor recurrence after definitive therapy. Rising post-treatment plasma EBV DNA has been shown to predate clinical recurrence by 3 to 7 months. Undetectable levels of plasma EBV DNA are observed in patients who remained in remission.

In a large ( $n=170$ ) NPC study in which most patients were treated uniformly with definitive RT (with only 15 patients also receiving weekly CDDP at  $40\text{mg}/\text{m}^2$  during RT), the levels of post-treatment plasma EBV DNA strongly predicted for progression-free survival (PFS) ( $p<0.001$ ) and OS ( $p<0.001$ ), and this post-treatment EBV DNA dominated the effect of pre-treatment EBV DNA. The 1-year PFS was 93% among patients with post-treatment EBV DNA  $\leq 500$  copies/mL, and 48% for those with  $> 500$  copies/mL.

A quantitative plasma EBV DNA assay was developed as an international harmonization study to facilitate EBV biomarker trials. Post-harmonization, the intraclass correlations for each site compared to the index site were 0.83 (0.5-0.95), 0.95 (0.83-0.99) and 0.96 (0.86-0.99),

respectively. The centers in this study will use an assay harmonized among the participating sites.

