### **2.2 Secondary**

- To determine the clinical response as judged by the investigator;
- To determine the overall response rate at 1 year from completion of therapy, as determined by RECIST 1.1 criteria;
- To determine the locoregional control rate at 1 year post-treatment;
- To determine the distant metastasis rate at 1 year post-treatment;
- ;
- To determine the rate of EBV DNA clearance at end of chemoradiation and at 1 year post-treatment;
- To determine the acute and late toxicity rates according to CTCAE v5.0, including immune-related adverse events (AEs);
- To assess patients' quality of life from baseline through 1 year post-treatment

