### 3.7 Duration of Follow Up

Patients will be followed for safety assessments for 100 days after completion of treatment or removal from study, or until death, whichever occurs first. All SAEs must be collected that occur within 100 days of discontinuation of dosing. Patients removed from study for unacceptable treatment related adverse event(s) will be followed until resolution or stabilization of all treatment related adverse events to Grade 2 or lower. Patients will be followed for adverse events for up to 1 year. Survival and disease status information may also be collected from review of the electronic medical records, patient visits, or telephone calls. Survival and disease status will be collected until participant death, withdrawal, or if the participant is lost to follow-up.

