a Each 14-day period of treatment will represent 1 cycle and begins from C1D1.b Baseline conditions assessmentc As part of efficacy assessments, quality of life by FACT-NP, FACT-Taxane, HHIE-S, and EuroQOL EQ-5D will be administered at baseline, at cycle 6, at end of treatment and at all followup visits. Survey's not available in the patient's language may be administered by the study staff in an interview format with a translator, however failure to obtain any individual quality of life survey not available in the patient's language will not be considered a protocol deviation.d Toxicity will be assessed by CTCAE v5.0f There is a 72 hour window of scheduled nivolumab administration. **In Dose Schedule 1:** Nivolumab will be administered on C1D1 for priming and then q14 days beginning C2D1, concurrent with chemoradiation, until C5D1. Nivolumab will not be administered on C6D1 to allow for any resolution of toxicities. Beginning C7D1, adjuvant nivolumab q14 days will be administered until C12D1. **In Dose Schedule 2:** Nivolumab will be administered on C1D1 concurrent with chemoradiation (no priming), and then q14 days until C4D1. Nivolumab will not be administered on C5D1 to allow for any resolution of toxicities. Beginning C6D1, adjuvant nivolumab q14 days will be administered until C11D1. **In Dose Schedule 3:** Nivolumab will not be administered until after completion of chemoradiation. Beginning C6D1, adjuvant nivolumab q14 days will be administered until C11D1. Immune-related toxicities should be at grade 1 or lower prior to starting a patient on the adjuvant phase of therapy; if not, initiation of the adjuvant phase should be delayed until resolution of toxicities.h Physical Exam includes weight measurementsi Disease-specific criteria (for CRF purposes, e.g.: GU assessment, BR disease Eval, AML-MDS Summary, etc.)j Measurable disease will be assessed using RECIST 1.1 criteriak For the **baseline** tissue collection, if a biopsy was performed within 90 days prior to C1D1, and no intervening treatment was given, a repeat biopsy is not required if adequate tumor tissue can be provided. **Repeat biopsy** will be at the discretion of the investigator, and timing will depend on Dose Schedule. **In Dose Schedule 1:** Tumor tissue post-nivolumab during cycle 1 AND after first week of radiation therapy. **In Dose Schedule 2 and 3:** Tumor tissue after first week of radiation therapy only. See appendix 4 for further details.l All blood draws may be completed within 7 days prior to start of therapy unless otherwise specified; screening labs must be completed within 14 days of Cycle 1 Day 1.m Hemoglobin, hematocrit, platelets, total white blood cell count (WBC) and differentialn Alkaline phosphatase, aspartate aminotransferase/alanine aminotransferase (ALT/AST), total bilirubin, total protein, albumin, calcium, phosphorus, magnesium, blood urea nitrogen (BUN), creatinine, glucose fasting), potassium, sodium, chloride, bicarbonate, uric acid, LDH, fasting lipid panel (LDL, total cholesterol, triglycerides), thyroid stimulating hormone (TSH).o **Pre-menopausal females:** serum or urine pregnancy test within 7 days prior to start of study drug. Serum pregnancy test by local laboratory  $\leq$  1 day prior to C1D1 for women of childbearing potential. If the serum pregnancy test results are not available on C1D1, a urine pregnancy test can be performed on C1D1 to confirm that the patient is not pregnant prior to dosing.p See Appendix 4 for details on tissue specimen collection and processing.q Collection of peripheral blood for correlative biomarkers and peripheral immune changes must be collected with every cycle of nivolumab. Blood will also be collected in post-treatment followup to 1 year.r Imaging with MRI nasopharynx/face/neck and whole body PET-CT will be performed at screening and at end of treatment and at 1 year followup, with further imaging to be performed as clinically indicated.

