
- If a whole body PET-CT (top of head to mid-thigh) scan (preferred) or a CT of the chest, abdomen, and pelvis was performed within 60 days prior to C1D1, then a repeat scan is not required provided the images are adequate for analysis. PET-CT is required after protocol treatment completion.

- MRI scan of nasopharynx/face/neck required within 60 days prior to C1D1 and after protocol treatment completion.
- sAll patients to be followed for safety until the EOT visit. This visit should occur 28 (+/-7) days after the last dose of nivolumab. Patients with ongoing SAEs will be followed until either resolution or stabilization of the event(s) have been determined.
- tAfter completion of all treatment, patient will be followed at 1, 3, 6, 9 and 12 months +/- 1 week for up to 1 year.
- uFasting lipid panel and TSH blood tests will not be performed on day 8. Only CBC with differential and blood chemistry tests including non-fasting glucose are required on day 8 of Cycles 2, 3, and 4.
- vSurvival follow-up information may be collected via telephone calls, and/or review of the medical record, every 3 months for an additional 4 years. Survival and disease status will be collected until participant death, withdrawal, or if the participant is lost to follow-up.

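### Section 6.1.4 ends follow-up visits at progression while the Abstract and Table 6.1 do not, which leaves the 1-year EBV clearance rate open to upward bias

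*Combined protocol and SAP*

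**What the plan says.** Section 6.1.4 sets the post-treatment visits: "patients will be followed at 1, 3, 6, and 12 months +/- 1 week for up to 1 year or until disease progression". It lists EBV DNA blood, quality of life, MRI, PET-CT and adverse event monitoring among the visit procedures, and refers to Table 6.1 for details.

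Table 6.1, footnote t, sets the same visits differently: "patient will be followed at 1, 3, 6, 9 and 12 months +/- 1 week for up to 1 year". The Abstract also lists months 1, 3, 6, 9 and 12. Footnote q takes blood in follow-up to 1 year, and footnote r schedules MRI and PET-CT at 1 year. Under footnote c the questionnaires "will be administered at baseline, at cycle 6, at end of treatment and at all followup visits". None of these has a progression stop.

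A secondary objective in Section 2.2 is: "To determine the rate of EBV DNA clearance at end of chemoradiation and at 1 year post-treatment". Appendix 4 reserves the purple-top tube for EBV DNA and draws it at baseline, at cycle 7 day 1 and at the 12-month visit. The draws at treatment discontinuation and at months 1, 3, 6 and 9 are green-top only. Section 1.4.2 states: "Undetectable levels of plasma EBV DNA are observed in patients who remained in remission". It adds that rising EBV DNA comes 3 to 7 months before clinical recurrence.

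Section 8.4.3 describes analyses of response, locoregional control and distant metastasis. It gives none for EBV clearance or quality of life, and so no denominator and no rule for missing samples.

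**The concern.** Two current passages give sites different instructions for patients who progress in the first year. Under 6.1.4 their visits stop; under footnote t they continue. In a multicentre trial the pattern of missing data could therefore vary by site.

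The 1-year EBV endpoint is the most exposed, because Appendix 4 gives it one sampling time and no tube at progression. On the protocol's own account, the patients who would lose that sample are those most likely to have detectable EBV DNA. With no stated denominator, nothing in the plan prevents the rate from being calculated only in patients who reached month 12 without progression. That figure would say little about whether the regimen clears EBV DNA in the patients treated. Quality of life after progression and the scheduled 12-month scan would be lost in the same patients.

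**Working it through.** The plan states no expected clearance rate or progression rate, so there is no figure of its own to reproduce. The check sets the rules side by side and then sizes the possible bias under stated assumptions.

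**Rules for a patient who progresses before month 12**

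| Item | Under 6.1.4 | Under the Abstract and Table 6.1 |
|---|---|---|
| Visits | Stop at progression; no month 9 in the list | Months 1, 3, 6, 9, 12 |
| 12-month EBV tube | Not drawn | Drawn (Appendix 4) |
| Questionnaires | Stop with the visits | All follow-up visits |
| 12-month MRI and PET-CT | Not scheduled | Scheduled (footnote r) |

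**Size of the bias in 1-year EBV clearance**

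Let d be the share progressing by month 12, c0 the clearance rate in progression-free patients and c1 the clearance rate in progressors.

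- Rate among sampled patients only = c0
- Rate among all patients = (1 − d) × c0 + d × c1
- Overstatement = d × (c0 − c1)

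Assumed ranges: d 5–30%, c0 90–100%, c1 0–50%.

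- Smallest: 0.05 × (0.90 − 0.50) = 2 points
- Largest: 0.30 × (1.00 − 0) = 30 points

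Examples with c0 = 95% and c1 = 25%:

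| d | Sampled only | All patients | Overstatement |
|---|---|---|---|
| 10% | 95% | 0.90 × 95 + 0.10 × 25 = 88.0% | 7.0 points |
| 15% | 95% | 0.85 × 95 + 0.15 × 25 = 84.5% | 10.5 points |
| 25% | 95% | 0.75 × 95 + 0.25 × 25 = 77.5% | 17.5 points |

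**A rough bracket for d**

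Section 1.4.2 cites 1-year progression-free survival of 93% at or below 500 copies/mL and 48% above. Assume that 80% to 100% of patients are at or below that level.

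- At 80%: 0.80 × 93 + 0.20 × 48 = 84%, so 40 × 0.16 = 6.4 events in 40 patients
- At 100%: 93%, so 40 × 0.07 = 2.8 events in 40 patients

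That is about 3 to 6 of the maximum 40 evaluable patients. The cited cohort was treated mostly with radiation alone, and such events normally include deaths, which yield no 12-month sample under any schedule. The bracket is only an order of magnitude.

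**Dependence on the denominator**

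If a missing sample counts as not cleared, the rate is (1 − d) × c0. With d = 10% and c0 = 95% this is 85.5%, below the 88.0% in all patients. The upward bias is gone.

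**The case against.** The strongest reply is that 6.1.4 is one passage against several. It refers to Table 6.1 for detail, and the table covers all patients to 12 months. On that reading the data would be collected and only a wording slip remains. This stands in part: the documents do not support a flat statement that 12-month data will exist only for progression-free patients. But 6.1.4 is the operative text on these visits and its stop is explicit, so a site could follow it in good faith.

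Second, a reader might infer that EBV clearance will be reported near 100%. That needs a sampled-only denominator, which the plan neither adopts nor excludes, together with near-complete clearance in progression-free patients. The direction of the bias follows from Section 1.4.2; the size does not follow from any figure in the documents.

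Third, a reader might extend the point to late toxicity. Section 3.7 says "Patients will be followed for adverse events for up to 1 year", with no progression stop. The Abstract's reporting window "ends 12 months following the last administration of study treatment or study discontinuation/termination, whichever is earlier" could close sooner for a patient who leaves the study, but that is not a stop at progression.

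Fourth, a reader might infer that distant metastases after locoregional failure will be censored or under-counted. Section 8.4.3 states no such censoring rule and counts any documented distant progression or death. The Abstract adds: "Survival and disease status will be collected during this 5-year period until participant death, withdrawal, or if the participant is lost to follow-up". Losing the scheduled scan may make detection less uniform, but under-counting is not shown.

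Finally, values taken after progression may reflect later therapy, so stopping collection at progression can be defended. That is a choice of estimand, which the plan would need to state; at present it states none.

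**Conclusion.** The contradiction is real and needs reconciling. Sections 6.1.4 and Table 6.1 disagree on whether visits continue after progression and on whether there is a month-9 visit. If 6.1.4 is followed, the 12-month EBV sample, later questionnaires and scheduled 12-month imaging are missing because of progression.

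For EBV clearance, the consequence is an upward bias of d × (c0 − c1) if only sampled patients are counted: about 2 to 30 points over the assumed ranges, and 7 to 10.5 points at 10–15% progression with c0 = 95% and c1 = 25%. All three inputs are assumptions.

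The point is limited to secondary endpoints. Adjuvant completion, the primary endpoint, is untouched. So is EBV clearance at the end of chemoradiation, whose sample is taken before the adjuvant phase.

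**What to change.** 1. In 6.1.4, remove the progression stop for data collection and add month 9, so that the section matches footnote t and the Abstract. Living, consenting patients then keep the 12-month EBV sample, the questionnaires and the imaging already planned in Table 6.1.
2. In 8.4.3, define 1-year EBV clearance. Use patients with detectable baseline EBV DNA as the denominator, and count those who progressed or died without a 12-month sample as not cleared. Report the sampled-only rate as a sensitivity analysis.

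The second change is needed even if the first is made, because deaths and missed visits will still leave gaps.

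The cost is a few visits and tubes in patients who progress, plus a scan that Table 6.1 already schedules. Some values will reflect later therapy. The clearance figure will be less favourable than a sampled-only rate, and it is conservative if some unsampled progressors had in fact cleared.

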### **6.1.5 Long Term/Survival Follow-up Procedures**

Survival follow-up information may be collected via telephone calls or medical records review for an additional 4 years. Survival and disease status will be collected during this period until participant death, withdrawal, or if the participant is lost to follow-up. .

### **6.1.6 Discontinuation of Therapy**

The Investigator will withdraw a patient whenever continued participation is no longer in the patient's best interests. Reasons for withdrawing a patient include, but are not limited to, disease progression, the occurrence of an adverse event or a concurrent illness, a patient's request to end participation, a patient's non-compliance or simply significant uncertainty on the part of the Investigator that continued participation is prudent. There may also be administrative reasons to terminate participation, such as concern about a patient's compliance with the prescribed treatment regimen.

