### **Dosing Delays for General and Immune-Related Adverse Events**

Algorithms in tables which follow and Appendix 5 should be consulted for specific immune-related AEs and followed preferentially rather than this general guideline.

Grade of Event	Management/Next Dose for Nivolumab
≤ Grade 1	No change in dose
Grade 2	Hold until ≤ Grade 1 Resume at same dose schedule when toxicity ≤ Grade 1
Grade 3	Hold* until ≤ Grade 2 Resume at same dose schedule when toxicity ≤ Grade 2
Grade 4	Off protocol therapy

\*Patients requiring a delay of > 28 days should go off protocol therapy

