Patients with persistent symptoms greater than 14 days who require steroids should be taken off study treatment.	
Please evaluate pituitary function prior to starting steroids if possible without compromising acute care.	
Evaluation for all patients for additional causes includes C. diff , acute and self-limited infectious and foodborne illness, ischemic bowel, diverticulitis, and IBD.	

Pancreatitis	Management/Next Dose for Nivolumab
Amylase/Lipase	
$\leq$ Grade 1	Hold dose until grade 0.

Grade 2	Hold until Grade 0. Resume at same dose schedule if asymptomatic.
Grade 3	Hold* until Grade 0. Resume at same dose schedule if asymptomatic. Patients who develop symptomatic pancreatitis or DM should be taken off treatment.*
*Grade 4	Off protocol therapy
	Patients may develop symptomatic and radiologic evidence of pancreatitis as well as DM and DKA. Lipase elevation may occur during the period of steroid withdrawal and with other immune-mediated events or associated with colitis, hepatitis, and patients who have asymptomatic lipase elevation typically have self-limited course and may be retreated. For treatment management of symptomatic pancreatitis please follow the Hepatic Adverse Event Management Algorithm (in Appendix 5).
	*Excluding asymptomatic amylase and lipase increases

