**Management/Next Dose for Nivolumab**

Hold dose pending evaluation and resolution to ≤ Grade 0 or baseline including baseline pO2. Resume no change in dose after pulmonary and/or ID consultation.

Grade 2

Hold dose pending evaluation. Resume no change in dose after pulmonary and/or ID consultation if lymphocytic pneumonitis is excluded. Off study if grade 2 symptoms do not improve or worsen after 2 weeks of steroids and dose delay; see guidelines for management in Appendix 5.

Grade 3

Off protocol therapy; see guidelines for management in Appendix 5.

Grade 4

Off protocol therapy; see guidelines for management in Appendix 5.

Distinguishing inflammatory pneumonitis is often a diagnosis of exclusion for patients who do not respond to antibiotics and have no causal organism identified including influenza. Most patients with respiratory failure or hypoxia will be treated with steroids. Bronchoscopy may be required and analysis of lavage fluid for lymphocytic predominance may be helpful. Patients with new lung nodules should be evaluated for sarcoid like granuloma. Please consider recommending seasonal influenza killed vaccine for all patients.

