**Management/Next Dose for Nivolumab**

No change in dose.

Hold dose pending evaluation and observation. Hold until ≤ Grade 1; see guidelines for management in Appendix 5. Resume at same dose schedule for peripheral isolated n. VII (Bell's palsy); see guidelines for management in Appendix 5.

Off protocol therapy; see guidelines for management in Appendix 5.

Off protocol therapy; see guidelines for management in Appendix 5.

\*Patients with any CNS events including aseptic meningitis, encephalitis, or myopathy, peripheral demyelinating neuropathy, cranial neuropathy (other than peripheral n. VII), GB syndrome, myasthenia gravis should be off study.

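### Stopping treatment is not separated from leaving the study, so the plan permits 1-year locoregional and metastasis outcomes to go uncollected after an adverse event or progression.

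*Combined protocol and SAP*

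**What the plan says.** **Who is withdrawn.** Section 6.1.6 has the investigator withdraw a patient when continued participation no longer serves that patient's interests: "Reasons for withdrawing a patient include, but are not limited to, disease progression, the occurrence of an adverse event or a concurrent illness". The list goes on to the patient's own request, non-compliance and investigator uncertainty. It does not say whether follow-up continues.

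**What withdrawal ends.** Section 3.7: "Survival and disease status will be collected until participant death, withdrawal, or if the participant is lost to follow-up". Section 6.1.5: "Survival and disease status will be collected during this period until participant death, withdrawal, or if the participant is lost to follow-up". The abstract and Table 6.1 footnote v use the same end points. None confines withdrawal to withdrawal of consent.

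**What is kept after removal for toxicity.** Section 3.7: "Patients removed from study for unacceptable treatment related adverse event(s) will be followed until resolution or stabilization". The same section gives 100 days of safety follow-up after completion or removal, and adverse event follow-up for up to 1 year. Section 7.5 likewise follows the event. Neither section names disease assessment for patients removed from the study.

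**Toxicity wording in 5.2.1.** Two entries refer to the study. The grade 2 pneumonitis rule reads "Off study if grade 2 symptoms do not improve or worsen after 2 weeks of steroids and dose delay", and the neurologic footnote ends "GB syndrome, myasthenia gravis should be off study". The other entries refer to treatment, for example "Patients requiring a delay of > 28 days should go off protocol therapy" and, for colitis, "Patients with persistent symptoms greater than 14 days who require steroids should be taken off study treatment".

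**Visits.** Section 6.1.3 keeps all patients to the end-of-treatment visit, 28 (± 7) days after the last nivolumab dose, with MRI and PET-CT. Section 6.1.4 then stops the follow-up visits at progression. Table 6.1 footnote t runs them to 12 months with no such stop.

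**The concern.** Locoregional control and distant metastasis at 1 year post-treatment are secondary objectives. Section 8.4.3 estimates both by Kaplan-Meier, counts death from any cause as an event in each, and gives no rule for patients who leave before an event. Kaplan-Meier treats a patient who leaves as having the same later risk as those who stay. That is doubtful when the reason for leaving is toxicity that cut treatment short, or progression at another site.

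Two groups are exposed:

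- **Patients withdrawn for an adverse event with no prior failure.** Any later relapse, metastasis or death may go unrecorded.
- **Patients who progress.** The event at the progressing site is already counted. What can be lost is later failure at the other site, and death, which counts in both endpoints.

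Outcomes not collected after exit may not be recoverable at analysis.

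**Working it through.** The plan states no expected withdrawal rate and no figure for this loss, so there is nothing to reproduce. The check has two parts.

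**1. Can a patient leave under the text before 1 year?**

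| Step | Section | Result |
|---|---|---|
| Adverse event on nivolumab | 6.1.6 | Investigator may withdraw the patient from participation |
| Last dose given | 6.1.3 | Kept to the end-of-treatment visit, 28 (± 7) days later |
| After that visit | 3.7, 7.5 | For removed patients, only safety follow-up is named |
| Disease and survival status | 3.7, 6.1.5, footnote v | Collection ends at withdrawal |
| Progression instead | 6.1.4 against footnote t | One stops visits; the other does not |

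No section clearly keeps a withdrawn patient in disease follow-up beyond the end-of-treatment visit. The abstract's general aim of following patients for 1 year after treatment does not address them. Section 3.6 does use withdrawal of consent as a separate term, so the narrower wording was available.

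**2. How large could the effect be?**

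Inputs: maximum N = 40 (3.4, 8.2.1) and expected completion 70% (8.2.1). Expected non-completers are 0.30 × 40 = 12. The event risks below are assumptions; the documents give none for these groups.

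*Bounds.* If m of 40 patients have no 1-year outcome, the worst case counts all m as failures and the best case counts none. The width is m/40, whatever the risks.

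| Lost (m) | Width | Illustration (assumed results among retained) |
|---|---|---|
| 4 | 4/40 = 10 points | 32 of 36 event-free: 32/40 = 80% to 36/40 = 90% |
| 8 | 8/40 = 20 points | 29 of 32 event-free: 29/40 = 72.5% to 37/40 = 92.5% |
| 12 | 12/40 = 30 points | 25 of 28 event-free: 25/40 = 62.5% to 37/40 = 92.5% |

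*Bias.* If a fraction f is lost and contributes no events, bias = f × (risk in lost − risk in retained). With an assumed 1-year metastasis risk of 8% among retained patients:

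| Lost | Risk in lost | True rate | Understatement |
|---|---|---|---|
| 12 (30%) | 8% | 8.0% | 0 |
| 12 (30%) | 12% | 0.7 × 8 + 0.3 × 12 = 9.2% | 1.2 points |
| 12 (30%) | 20% | 0.7 × 8 + 0.3 × 20 = 11.6% | 3.6 points |
| 6 (15%) | 20% | 0.85 × 8 + 0.15 × 20 = 9.8% | 1.8 points |
| 4 (10%) | 20% | 0.9 × 8 + 0.1 × 20 = 9.2% | 1.2 points |

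The 3.6 points equal 0.036 × 40 ≈ 1.4 patients. For scale, the standard error of 11.6% with n = 40 is √(0.116 × 0.884 / 40) ≈ 5.1 points.

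At any given pair of risks the formula overstates the bias. The clock in 8.4.3 starts on the first day of treatment, so time and events before exit count, including findings on end-of-treatment imaging.

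**The case against.** The strongest reply is that withdrawal means the participant's own withdrawal. Section 3.6 lists withdrawal of consent, progression and adverse events as separate reasons to stop nivolumab, and 6.1.2 names subject withdrawal apart from toxicity and progression. Section 6.1.6 is headed as discontinuation of therapy, and Appendix 4 takes the cycle 7 blood sample whether or not nivolumab is given. On that reading, nobody leaves for toxicity alone. It is a reasonable reading and may be what the authors intended. But 6.1.6 is where investigator withdrawal is described, its text concerns participation, and the sections that end collection do not choose between the two meanings. The ambiguity stands.

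Four stronger inferences are tempting, and the documents do not support them:

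- *That the toxicity tables generally remove patients from the study.* Only two entries do; beside both, the grade 3 and 4 rows stop protocol therapy only.
- *That late immune toxicity is lost.* Section 3.7 gives 100 days of safety follow-up after removal and up to 1 year for adverse events.
- *That the 1-year survival analysis is biased.* One-year survival is an objective only in the abstract. The body has survival as exploratory at 5 years, and 8.4.3 specifies no survival analysis.
- *That all 12 non-completers vanish without an event.* Non-completion includes progression, which is already an event at its site, and not everyone who stops would be withdrawn.

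Nor do the documents show that early stoppers carry higher risk. That is plausible but assumed, and a zero difference belongs in the range.

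**Conclusion.** The concern holds as a gap that permits loss of outcomes, not as a rule that requires it. Followed literally, the plan lets a patient withdrawn for toxicity leave disease follow-up after the end-of-treatment visit, and lets a patient with progression lose later failure at the other site and later death. Censoring in the two Kaplan-Meier analyses could then be informative.

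The size depends on how many leave and on risks the documents do not give. The bounds widen by 2.5 points per patient lost (1/40). The bias ranges from zero, when risks are equal, to at most about 3.6 points at 20% versus 8% with all 12 expected non-completers lost. That last case is an upper scenario for those risks; a larger difference in risk would give more.

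The primary endpoint is not affected, because completion of adjuvant nivolumab is known when nivolumab stops. The change is still worth making, because it costs little.

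**What to change.** 1. **6.1.6:** separate discontinuation of protocol therapy from withdrawal from the study. Keep the patient's own request to end participation under withdrawal, so that it is not relabelled as a therapy stop.
2. **3.7, 6.1.5 and 6.1.6:** add, for example: *Patients who stop protocol therapy for any reason, including progression, remain in scheduled disease, safety and survival follow-up unless they withdraw consent to follow-up or are lost.* Carry the same meaning of withdrawal into the abstract and footnote v.
3. **5.2.1:** reconcile the study-status wording of the pneumonitis grade 2 entry and the neurologic footnote with the protocol-therapy wording used elsewhere. No toxicity or stopping rule changes, and no view is taken on them.
4. **6.1.4 and Table 6.1 footnote t:** reconcile whether visits continue after progression.

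It would also help to state the censoring rule in 8.4.3 and to report how many patients leave without a 1-year outcome, with the best/worst-case bounds.

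The cost is an amendment to wording. The visits, scans and calls are already in the schedule; the added work is carrying them out for patients who would otherwise have left.
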